10.41 Grading Scale for other toxicities

Telangiectasia: Grade 0 – None; Grade 1 – 1cm²; Grade 2 – 2-4cm²; Grade 3 - >4cm²

10.5 Monitoring and Auditing

The investigator will permit study-related monitoring, audits, and inspections by the IRB, internal regulatory areas, and government regulatory agencies, of all study related documents (e.g. source documents, regulatory documents, data collection instruments, study data etc.). The investigator will ensure the capability for inspections of applicable study-related facilities (e.g. pharmacy, diagnostic laboratory, etc.).

Participation as an investigator in this study implies acceptance of potential inspection by government regulatory authorities and applicable compliance offices

10.51 Medical Monitoring

It is the responsibility of the Principal Investigator to oversee the safety of the study at his/her site. This safety monitoring will include careful assessment and appropriate reporting of adverse events as noted above, as well as the construction and implementation of a site data and safety-monitoring plan (see section 10.5 “Monitoring and Auditing”). Medical monitoring will include a regular assessment of the number and type of serious adverse events. “Any serious adverse events will be followed up by the sentinel event reporting procedure”

10.52 Internal Data and Safety Monitoring

The trial will be reviewed by the Cancer Center Auditing area on a bi-annual or yearly basis dependent on random study selection to assess accrual, adverse events, and any endpoint problems. Any safety issues requiring protocol changes will be communicated through protocol amendments.

11.0 Treatment Evaluation

11.1 Patients will be evaluated at baseline, then in follow-up according to the Assessment Schedule (Section 4.0)

11.2 At the time of reevaluation, patients will be classified in the following manner:

11.21 No evidence of disease (NED).

11.22 Recurrence of disease (REC). Recurrence must be confirmed by biopsy.

11.221 The site of recurrence (or failure) will also be collected and classified as local vs. regional vs. distant recurrence. The specific site of failure will also be collected as well. Moreover, if there is an IBTR, the location of the IBTR relative to the initial cancer will be documented and the IBTR will be classified according to Recht et al. as a “true recurrence/marginal miss” failure if the recurrence of the treated cancer occurs within or immediately adjacent to the primary tumor site. An “Elsewhere Failure” will be defined as an IBTR several centimeters from the primary site.

11.222 Secondary Treatment. The date of the first retreatment and extent of retreatment post-recurrence (i.e. secondary resection or re-irradiation for primary disease), will be collected. Pathology, if available, and operative reports are required to be submitted per Section 18.0.

11.3 Cosmesis evaluation and Patient Reported Outcomes

11.31 Digital photographs should be performed according to the schedule outlined in section 4.0 and should include three poses: from the front with hands on hips and both lateral views. Recommended framing should go from the sternal notch to the umbilicus. If possible, patients should be photographed against a solid colored background.

11.32 The Harvard Cosmesis Scale will be used to score cosmesis according to the schedule outlined in section 4.0. The patients will be assessed as one of the following:

- Excellent: treated breast nearly identical to untreated breast
- Good: Treated breast slightly different than untreated (minimal but identifiable effects of the treated breast)

- Fair: Treated breast clearly different from untreated but not seriously distorted (significant radiation effects readily observable)
- Poor: Treated breast seriously distorted (severe sequelae of breast tissue secondary to radiation effects)

A modified version of the Harvard Cosmesis Scale will also be used for patient reported assessment of cosmesis.

11.33 The Breast Cancer Treatment Outcome Scale (BCTOS) is a self-report instrument that has high reliability and validity and will be used for evaluating patient-rated cosmesis according to the schedule outlined in section 4.0.

11.34 Patient-Reported Outcomes Version of the Common Terminology Criteria for Adverse Events (PRO-CTCAE) will be used for patient self-reporting of toxicities in the CTCAE.

11.35 Other Patient Reported Outcome questions (fatigue, pain, arm function etc.) included in the appendix.

12.0 Descriptive Factors

- Breast Quadrant: upper inner, upper outer, lower inner, lower outer
- AJCC Stage
- Tumor Size
- Invasive vs non-invasive

13.0 Treatment/Follow-up Decision at Evaluation of Patient

13.1 Patients who have a recurrence while receiving therapy or during observation will go to the event-monitoring phase and be followed.

13.2 Patients who discontinue treatment or observation for reasons other than recurrence will go to the event-monitoring phase and be followed.

13.3 Patients that complete all adjuvant treatment will then be followed during the observation phase as outlined in section 4.0.

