16.61 *Acute adverse events (up to 90 days post-RT):* All patients who were registered to the study and started treatment will be included in the acute adverse event analysis. An acute adverse event is an AE, regardless of attribution, that occurs up to 90 days post-RT. The maximum grade for each type of acute AE will be recorded for each patient. Data will be summarized as frequencies and relative frequencies. Additionally, the relationship of the adverse event(s) to the study treatment will be taken into consideration.

16.62 *Late adverse events:* All patients who were registered to the study and started treatment will be included in the late adverse event analysis. A late adverse event is an AE, regardless of attribution, that occurs at least 90 days post-RT and up to 3 years post-RT. The maximum grade for each type of late AE will be recorded for each patient. Data will be summarized as frequencies and relative frequencies. Additionally, the relationship of the adverse event(s) to the study treatment will be taken into consideration. Prior APBI reports have suggested rates of grade 3 or 4 toxicity to be $\leq 10\%$.^{18,47,55,56}

16.63 *Quality of life:* The QOL measurements will be summarized at each time point as mean \pm SD and median (minimum value, maximum value). Changes in the QOL measurements from baseline will be determined at each follow-up measurement. These will be displayed as spaghetti plots. The assessment of the changes at each time point will be done with a paired t-test or Wilcoxon signed rank test, whichever is appropriate.

16.64 *Cosmesis*: The values of the cosmesis instruments (patient self-reported and panel-assessed) will be summarized with the frequencies of fair or poor cosmesis events at baseline and 3 years, and the difference at 3 years, as well as their relative exact binomial confidence intervals.

16.65 *IBTR incidence*: The IBTR cumulative incidence will be estimated using a competing risks method (Gooley et al.). The competing risks will be regional/distant breast cancer recurrence and death.

16.66 *Regional recurrence incidence*: The regional breast cancer recurrence cumulative incidence will be estimated using a competing risks method (Gooley et al.). The competing risks will be local/distant breast cancer recurrence and death.

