16.9 Data & Safety Monitoring

16.91 The principal investigator(s) and the study statistician will review the study at least every quarter to identify accrual, adverse events, and any endpoint problems that might be developing. The Mayo Clinic Cancer Center (MCCC) Data Safety Monitoring Board (DSMB) is responsible for reviewing accrual and safety data for this trial at least twice a year, based on reports provided by the MCCC Statistical Office.

16.92 Adverse Event Stopping Rules: The stopping rules specified below are based on knowledge available at study development. We note that the Adverse Event Stopping Rule may be adjusted in the event of either (1) the study re-opening to accrual or (2) at any time during the conduct of the trial and in consideration of newly acquired information regarding the adverse event profile of the treatment(s) under investigation. The study team may choose to suspend accrual because of unexpected adverse event profiles that have not crossed the specified rule below. The following rule will be evaluated for each arm separately.

Accrual will be temporarily suspended if at any time we observe events considered at least possibly related to study treatment (i.e. an adverse event with attribute specified as “possible,” “probable,” or “definite”) that satisfy one of the following:

- If 3 or more patients in the first 15 treated patients experience a grade 3 or higher adverse event, besides acute dermatitis, that is at least possibly related to treatment within 90 days post treatment..
- After the first 15 patients have been treated: if $\geq 20\%$ of all patients experience a grade 3 or higher adverse event, besides acute dermatitis, that is at least possibly related to treatment within 90 days post treatment.

Similarly, within each of the modalities (photon, proton, or brachytherapy APBI), accrual will be suspended for that modality:

- If 6 or more patients in the first 30 treated patients experience a grade 3 or higher adverse event at least possibly related to treatment at any time after 6 months following completion of the protocol treatment.
- After the first 30 patients have been treated: if $\geq 20\%$ of all patients experience a grade 3 or higher adverse event at least possibly related to

treatment at any time after 6 months following the completion of protocol treatment.

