18.0 Records and Data Collection Procedures

18.1 Submission Timetable

Initial Material(s) -

CRF	Treatment (Compliance with Test Schedule Section 4.0)
Institutional Contacts	
Patient Eligibility	
Demographics	
On-Study	≤2 weeks after registration
Adverse Events- Baseline	
Specimen Submission: Blood (Baseline)	
Specimen Submission: Tissue (Baseline)*	*6 months from accrual
Patient Status: Baseline	
Patient Assessment	
Off Treatment	Submit ≤2 weeks after registration if withdrawal/refusal occurs prior to beginning protocol therapy

Test Schedule Material(s)

CRF	Post Radiation (cycle 2)	Observation ³ (subsequent cycles)
Radiation Treatment Form	X	
Patient Assessment	X	X
Specimen Submission: Blood (post rad tx)	X	

CRF	Post Radiation (cycle 2)	Observation ³ (subsequent cycles)
Adverse Events Solicited	X	X
Adverse Events Other	X ¹	X ¹
Off Treatment: Submit once per patient	X ¹	
Patient Status form	X	X
Adverse Events: Late		X ¹
Specimen Submission: Tissue (Recurrence)		X ¹
Consent Withdrawal form	X ¹	X ¹
Lost to Follow-up	X ¹	X ¹
Breast/Chest Wall Radiotherapy Questionnaire	X	X

1. When applicable
2. Survey will need to be entered manually if has not alternately been scanned or entered electronically
3. Observation (Active monitoring phase): 12 weeks (+/- 4 weeks), 12 months (+/- 30 days), annually for 5 years (+/-3 months). If a patient is still alive 5 years after registration, no further follow-up is required.

Follow-up Material(s)

CRF	Event Monitoring Phase ¹	
	12 months	Annually for 5 years ²
Patient Status: Survival and Disease Status Follow-Up/Event Monitoring	X	X

1. If a patient is still alive 5 years after registration, no further follow-up is required.
2. If patient has a recurrence prior to being off radiation therapy for 5 years, continue to follow yearly.

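### No toxicity assessment is scheduled after a treated patient leaves treatment or observation or has a recurrence, yet she stays in the adverse-event denominators, so later non-serious grade 3 events may be missed

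*Combined protocol and SAP*

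**What the plan says.** **Routing.** Section 13.2: "Patients who discontinue treatment or observation for reasons other than recurrence will go to the event-monitoring phase and be followed". Toxicity is not excepted. Section 13.1 gives recurrence, during therapy or observation, the same route. Section 13.3 describes who enters observation: "Patients that complete all adjuvant treatment will then be followed during the observation phase as outlined in section 4.0".

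**Forms.** In section 18.1 the follow-up table for event monitoring has one row, "Patient Status: Survival and Disease Status Follow-Up/Event Monitoring", due at 12 months and then annually for 5 years. "Adverse Events Solicited" and the form for other adverse events are listed under Post Radiation and Observation. "Adverse Events: Late" is listed under Observation only, when applicable. Sections 18.24 and 18.26 add that forms are released on a preset visit schedule and that only the necessary ones are open for entry.

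**Analysis sets.** Section 16.61: "All patients who were registered to the study and started treatment will be included in the acute adverse event analysis". Section 16.62 uses the same set for late events: "A late adverse event is an AE, regardless of attribution, that occurs at least 90 days post-RT and up to 3 years post-RT".

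**Suspension rules (16.92).** For events within 90 days, accrual is suspended at 3 of the first 15 treated patients, then at 20% or more of all patients. For late events, within each modality, the limits are 6 of the first 30, then 20% or more, counting grade 3 or higher events at least possibly related to "treatment at any time after 6 months following the completion of protocol treatment".

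**The concern.** Read together, these sections keep a woman in the denominator after scheduled collection of her toxicity has ended. Her later record then holds only events that someone happens to identify and report. A woman with no entry is indistinguishable from a woman with no event.

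The error runs one way. Missing events lower the reported grade 3+ rates and make suspension less likely. The late rule is the more exposed, because it covers a long period in which patients can leave observation or have a recurrence. It also counts grade 3 events whether or not they are serious, and several of those are found by examination. Superficial fibrosis is on the list in 10.4 for grading at each evaluation. Telangiectasia is graded by area in 10.41, with grade 3 meaning more than 4 cm².

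**Working it through.** **1. What is scheduled, by phase (13.1 to 13.3, 18.1)**

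| Form | Post Radiation | Observation | Event monitoring |
|---|---|---|---|
| Solicited adverse events | yes | yes | not listed |
| Other adverse events | when applicable | when applicable | not listed |
| Late adverse events | not listed | when applicable | not listed |
| Survival and disease status follow-up | not listed | not listed | 12 months, then annually |

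The first event-monitoring form falls after the 90-day acute window. Its content is inferred from its title, since the form itself is not in the documents.

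**2. Who is counted.** 16.61 and 16.62 count all registered patients who started treatment; 16.92 counts treated or all patients. None of them removes or censors a patient who moves to event monitoring.

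**3. The plan's own limits.** 3/15 = 20% and 6/30 = 20%, which match the 20% used afterwards.

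**4. Effect on the late rule.** Inputs from 16.92: n = 30, limit 6. Assumptions, because the documents give no figure: a true grade 3+ rate p, and a share L of events that goes unrecorded. The recorded rate is p(1 − L), and the chance of triggering at 30 patients is P(X ≥ 6) with X ~ Binomial(30, p(1 − L)).

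| True rate p | L = 0 | L = 10% | L = 20% |
|---|---|---|---|
| 10% | 0.073 | 0.048 (rate 9%) | 0.029 (rate 8%) |
| 20% | 0.572 | 0.461 (rate 18%) | 0.345 (rate 16%) |
| 30% | 0.923 | 0.859 (rate 27%) | 0.760 (rate 24%) |

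**5. The same effect by number of patients.** Suppose m of the 30 are counted but can contribute no event, so that X ~ Binomial(30 − m, p). At p = 20%, P(X ≥ 6) is 0.572 for m = 0, 0.537 for m = 1 and 0.461 for m = 3. At p = 30% it is 0.923, 0.907 and 0.864.

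**6. The running 20% rule.** If a share u of patients is unobserved, 20% of all patients requires 0.20/(1 − u) among those observed: 20.4% at u = 2%, 21.1% at 5%, 22.2% at 10% and 25.0% at 20%.

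**7. The acute rule.** The rule counts patients, not events. A woman who stops because of a related grade 3+ event within its scope is already one of the 3, and her event can go on the Post Radiation forms, in the same column as the Off Treatment form. The rule can miss only a woman who leaves without a qualifying event, has one later within 90 days, and whose event is not identified by another route.

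**The case against.** **Other routes exist.** Section 10.3 is not tied to a phase. Any identified adverse event gets a worksheet whose fields are entered in the research database, and serious events go through the data capture system. Section 8.2 promises reporting of all detected toxicities, and 16.91 has the investigators and statistician review adverse events at least quarterly. This stands. A reader might infer that toxicity after early stopping cannot reach the analyses at all; 10.3 shows otherwise. But 10.3 acts once an event is known. It schedules no visit and no grading.

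**Stopping for toxicity.** A reader might also infer that the suspension rules are blind to the women with the worst early tolerance. The documents do not support that for the 90-day rule, for the reason in step 7. Treatment is only three fractions, and 8.2 calls severe acute toxicity extremely rare. Nor does 13.2 move a patient out of observation because she develops late toxicity, so the documents do not establish that late losses are driven by the outcome. They also do not show that losses differ by technique.

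**Existing fallback.** Footnote 7 of section 4.0 provides for outside records and mailed questionnaires when patients cannot return, and PRO-CTCAE collects patient-reported toxicity. This helps in part. The footnote itself concedes that scheduled items may not be captured, and a questionnaire cannot supply a clinician grade such as telangiectasia area.

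**Recurrence and withdrawal.** Ending toxicity grading at recurrence can be defended, since further surgery or re-irradiation confuses attribution. That applies from salvage treatment onward, not before it. For patients who withdraw consent or are lost, more forms would recover little.

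**Size.** The plan expects grade 3+ complications in under 10% of patients (8.2) and cites rates of at most 10% (16.62), so a true rate of 20% is a stress case. The late rule also has no effect once accrual has closed. Both points are fair.

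**Conclusion.** The concern holds in a limited form. Sections 13.1, 13.2 and 18.1 end scheduled toxicity assessment for a treated patient who discontinues treatment or observation or has a recurrence, while 16.61, 16.62 and 16.92 go on counting her. What may be lost is mainly later non-serious grade 3 toxicity. The bias is downward, in the late grade 3+ rates and the late suspension rule. The acute rule is affected only for patients who leave before a qualifying event.

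The size cannot be fixed from the documents. At an assumed true rate of 20%, an assumed 10% loss of events takes the chance of triggering 6 of 30 from 57% to 46%, and a 20% loss takes it to 35%. With few departures the effect is small: one unobserved patient in 30 costs about 4 points at a true rate of 20% (0.572 − 0.537 = 0.035). The figures assume independent patients, a common event rate, and no recovery of the lost events through 10.3. The change is worth making because it is cheap and the error can only favour continuing.

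**What to change.** Reconcile 13.1, 13.2 and 18.1 with 16.61, 16.62 and 16.92:

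- In 18.1, add the existing solicited, other and late adverse-event forms to the event-monitoring table, up to 3 years after radiation. Schedule them so that the 90-day window is also covered.
- In 13.1 and 13.2, state that this applies to any patient who received at least one fraction and has not withdrawn consent. After recurrence, collection continues until salvage breast treatment.
- Complete the forms from clinic visits or outside records, and record which source was used.

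The cost is protocol wording, activation of existing electronic forms in one more phase, and some extra data entry for a small number of patients. Clinician grading will stay incomplete where only outside records exist. Treatment does not change.

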14.0 Body Fluid Biospecimens

14.1 Summary Table of Research Blood and Body Fluid Specimens to be collected for this Protocol

Collection Tube	Volume to Collect per Tube (Number of Tubes to Collect)
-----------------	---------------------------------------------------------

Collection Tube	Volume to Collect per Tube (Number of Tubes to Collect)
EDTA tubes	10 mL (1)
No additive tubes (for Serum)	10 mL (1)

All patients will undergo a blood draw at baseline and following the final administered fraction of radiotherapy. Label specimen tube(s) with patient ID number, time and date blood is drawn.

- 14.2 BAP will process and store specimens per standard operating procedures.
- 14.3 Bloods will be collected prospectively and stored until funding sources have been secured to investigate exploratory analyses described in section 16.7

15.0 Drug Information

Not Applicable

16.0 Statistical Considerations and Methodology

- 16.1 Overview: This is a single arm phase II study evaluating the rate of adverse cosmesis (defined as fair or poor cosmesis) at 3 years, compared to baseline, of 3 fraction accelerated APBI. For the analysis of the primary endpoint, patients will be pooled across the three treatment techniques (photon, proton, and brachytherapy) as was done in the the NSABP B-39/RTOG 0413 national multi-institutional randomized control trial comparing APBI with WBI. The three techniques utilized are recognized as standard options for the delivery of APBI, and there is no evidence that any technique is superior to any other with commonly used dose and fractionation regimens.⁴ The primary endpoint is the difference from baseline in the percentage of patients with adverse cosmesis (fair or poor cosmesis) at 3 years. The intent is to determine whether the difference of adverse cosmesis rate is acceptable. Of interest is whether the 3 fraction accelerated APBI results in an unacceptable increase in the adverse cosmesis rate at the end of 3 years, compared to baseline. If it does not, then the 3 fraction accelerated APBI will be recommended for further study. If the change in adverse cosmesis rate is found to be unacceptable, then the recommendation would be to do no further studies of the 3 fraction accelerated APBI. In addition to adverse cosmesis, this study will assess many additional secondary endpoints including IBTR (both invasive and non-invasive IBTRs will be considered), acute and late toxicity profile, quality of life measures, and translational studies.

16.2 **Primary Endpoint:** The primary endpoint is the percentage difference in patients with adverse cosmesis (fair or poor cosmesis) at 3 years compared to baseline. Cosmesis will be assessed by a trained nurse provider using the Harvard Cosmesis Scale.

All patients meeting the eligibility criteria who have signed a consent form, and begun treatment will be considered evaluable for the primary endpoint.

16.3 **Secondary Endpoints:** The secondary aims of this study are to characterize acute and late adverse events, assess patient self-reported and panel-reported cosmesis, IBTR rate, and quality of life as well as exploratory comparisons of cosmesis, toxicity, and IBTR rate between the 3 techniques. In addition, regional recurrence rates, distant recurrence rates, invasive disease-free survival, and overall survival will be estimated for each patient group treated with APBI. Blood will be collected for future studies in order to examine molecular and genomic predictors of adverse cosmesis and late toxicity.

The following definitions are used for the secondary endpoints of interest:

- *Acute adverse events* (up to 1 month post-RT): any adverse event, regardless of attribution, that occurs in the first month post-RT.
- *Late adverse events* (up to 3 years post XRT): any adverse event that occurred after the first month post-RT and up to 3 years post-RT.
- *Patient Reported Outcomes/Quality of life:* the Patient-Reported Outcomes Version of the Common Terminology Criteria for Adverse Events (PRO-CTCAE) will be used for patient self-reporting of toxicities in the CTCAE, along with other measures of fatigue, pain, and arm function listed in the appendix.
- *Patient self-reported cosmetic outcomes:* the patient self-reported outcome will be assessed using a modified Harvard Cosmesis Scale in the Breast Cancer Treatment Outcome Scale (BCTOS).
- *Panel assessed cosmetic outcome:* in addition to patient self-reported and physician reported outcomes, cosmesis will be assessed by a panel of breast cancer medical providers using digital photographs. The Panel will be blinded to treatment allocation.
- *IBTR:* this is defined as local recurrence at 3 years from trial registration as a first event. IBTR is defined as both invasive and non-invasive breast cancer involving the same breast parenchyma as the original tumor.
- *Regional recurrence:* invasive breast cancer in the axilla, regional lymph nodes, chest wall, and skin of the ipsilateral breast.
- *Distant recurrence:* metastatic cancer that has either been biopsy confirmed or clinically diagnosed as recurrent invasive breast cancer.
- *Invasive disease free survival:* this is defined as the time from study registration until the occurrence of one of the events in a composite endpoint. This endpoint includes invasive IBTR, regional invasive breast cancer recurrence, distant breast cancer recurrence, death due to any cause, contralateral invasive breast cancer, and second primary non-breast invasive disease.
- *Overall survival:* is defined as the time from registration to death due to any cause.

